Services will be provided to clients as part of routine MOH service provision. No adverse events as a result of this study are anticipated. If complications arise during routine service provision, the regular mechanisms will be followed, such as contacting senior providers and initiating referrals.

2. If a Data Safety Monitoring Board (DSMB), or equivalent will be established, describe the following:
 - a. The DSMB membership, affiliation and expertise.
 - b. The charge or charter to the DSMB.
 - c. Plans for providing DSMB reports to the IRB.
3. Describe plans for interim analysis and stopping rules, if any.

D. Reporting unanticipated problems/adverse events (AE's) to the IRB (*all studies must complete this section*):

Describe your plan for reporting to the IRB and (if applicable) to the sponsor. Include your plan for government-mandated reporting of abuse or illegal activity.

NOTE: The IRB does not require submission for all AEs, only those that are unanticipated, pose risk of harm to participants or others, and are related to the study.

ADVERSE EVENTS EXPECTED & UNEXPECTED

- At baseline, study staff (or a designated provider onsite) will visit the study sites to scan registers for the three previous months to establish the baseline rate for maternal and early newborn deaths and fresh stillbirths. . .
- Every 2 weeks, the study team will obtain the maternity register scan from each facility. We will determine the number of deliveries, number of live births, and the number of maternal and early newborn deaths and fresh stillbirths. We will determine the appropriate rates and whether any are more than 10% above the expected/normal rate.
- A summary log will be created for recording the number of deliveries, births, and adverse maternal or newborn outcomes for each 2 week period. This log will have the woman's facility admission number id on it obtained from the register. If this log indicates that normal levels have occurred, this summary AE log will be submitted to IRB along with progress report.
- If the normal level is exceeded (>10% higher than the average monthly total from 3 months prior to the intervention), Jhpiego will prepare a severe adverse events (SAE) report and the SAE policy will take effect with expedited reporting to IRB.

REPORTING

- If any unanticipated problems or adverse events occur, the study team will follow JHSPH IRB policy no. 103.06, "Reports of Unanticipated Problems Involving Risks to Participants or to Others".
- Should any adverse event occur in relation to or at the time of the data collection, the data collectors will be trained to notify their team leader immediately by phone, who will notify the co-investigators in Kenya and the PI and headquarters co-investigators within 2 business days.

- If a **severe adverse event (SAE)** occurs, the study team will immediately inform the principal investigator and follow Jhpiego's SAE Policy. The SAE policy requires immediate notification of the Kenya Country Director, local PI and overall study PI and completion and submission of Jhpiego's SAE Report Form. The Country Director will then send the relevant documentation to the Jhpiego headquarters-based Medical Director and Contracts Administrative Manager. Advice will then be provided to the Country Director for next steps.
- A summary of unanticipated problems and AEs will be reported to JHSPH IRB in the annual progress report.
- Severe unanticipated problems will be reported to JHSPH IRB as soon as possible after the PI learns of the event, but not later than 10 days.

E. Other IRBs/Ethics Review Boards:

If other IRBs will review the research, provide the name and contact information for each IRB/ethics review board and its Federal Wide Assurance, if it has one (available on OHRP's website at <http://www.hhs.gov/ohrp/assurances>).

IORG0006771 - Kenya Medical Research Institute (KEMRI) , IRB00008118

[figure not shown]
[figure not shown]
[figure not shown]
[figure not shown]
[figure not shown]
[figure not shown]
Kenya Medical Research Institute (KEMRI)
KEMRI IRB00008118
[name]
[contact], Email: [contact] <http://www.kemri.org>

(for reporting of adverse events): The Secretary, KEMRI Ethics Review Committee, [name]; Telephone numbers: [name], [name], [name]; Email address: [contact]

[figure not shown]
[figure not shown]
ALL SECTIONS AFTER THIS ARE NOT APPLICABLE.

F.

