 - a. The training will be on routine labor monitoring and using the partograph as a decision-making tool. Facilities will receive stocks of any supplies and drugs that are needed for monitoring or normal labor and management of complications and referrals.
 - b. This training will cover how to fill out the Ministry of Health register on each woman/newborn.
 - c. ePartogram sites will also receive two days of training on using the Android-based ePartogram tablet 'app', maintaining the tablet computer, and standard operating procedures for tablet use and storage to

ensure data confidentiality. SBAs passing the ePartogram post-training test will be asked use the ePartogram during clinical care.

- 5) In both ePartogram and paper-partograph sites, **facility readiness** will be ensured. Enough copies of standard-of-care paper partographs will be available on site at facilities in both study groups, and supplies/equipment (i.e. blood pressure apparatus).
- 6) In **ePartogram** facilities:
 - a. Software support procedures if needed will be set up.
 - b. Standard Operating Procedures (SOPs) will be created for ownership of tablets, maintenance, and what to do in case of tablet malfunction or loss and Jhpiego's ongoing support.
 - c. Data coordinator will be on call to troubleshoot eP software questions
- 7) In **ePartogram** facilities, each participating provider will use the ePartogram tablet and application on women in labor.
 - a.) At ePartogram sites, all data entered into the ePartogram will automatically sync to the server when connected to the internet and saved to a secure, cloud-based, password-protected website. The partograph and outcome data will be accessed at least two times per week by the study coordinator.
 - b.) A designated onsite records-management staff or, in the absence of such staff, the nurse in-charge will take photographs of the Ministry of Health **register book**, weekly--where aspects of the care to a woman/newborn(s) are written in one row. This has info on the health outcomes.
 - c.) If paper partographs are used at ePartogram sites, this data will still be included in the ePartogram group.
- 8) In the **control sites**, the paper partograph will be used for labor monitoring/management. Providers will have available paper partographs, which is the standard of care for use during service delivery.

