 - a. In paper-partograph sites, every day onsite records-management staff or, in the absence of such staff, the nurse in-charge will take **scans of the partographs**. These will be scanned to password-protected study laptops and the files will be saved directly to a secure Dropbox to which only study staff will have access.
 - b. At paper-partograph sites, each week onsite records-management staff or, in the absence of such staff, the nurse in-charge will take photographs the Ministry of Health approved **register**.
- 9) At the office, the study coordinator and data clerks will monitor ePartogram and partograph data in the ePartogram website and paper partograph Dropbox.
 - a. For paper partographs, the photos or scans of partographs will be uploaded to a computer.
 - b. When visiting facilities, the study coordinator will orient providers on how to record in the MOH register book, if this is not occurring to standard.
 - c. The study training covers how to enter record in the partograph or ePartogram app. A Jhpiego clinical study manager will provide a one-on-one orientation to the ePartogram for any new staff. On site visits, the study coordinator will help validate the most recent register book info by comparing to the medical record if one exists and discussing any discrepancies with staff during weekly calls.
 - d. Register data photographed from both study groups will be saved to the office computer. At office, a data entry clerk will follow the 'abstraction tool' to enter register data to a database.
- 10) Partograph reviewers who are student interns from Johns Hopkins School of Public Health and Johns Hopkins University will be hired to review each partograph and enter data from the partograph and ePartogram records to the study's Partograph Extraction Tool (Revised) (see Study Implementation section).
- 11) The study coordination and analysis team will conduct an analysis of data **after 20 partographs and 20 ePartograms** for each site and thereafter after every 200-400 partographs. This will be to assess for completeness of data to know whether we are on track to answer the research questions.

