12) To answer the secondary research questions, starting in the second month after implementation, study manager will carry out **in-depth interviews** (or small focus group discussions) with providers at sites in both study groups. We will interview providers who use the paper partograph or the ePartogram to discuss barriers and facilitators to usage, including facility conditions. The supervision for providers around the ePartogram and paper-partograph use will also be explored. The interviews will be audio-recorded to capture all contributions from participants. Participants will be informed about this during consenting. The digital recorders erased/audio tapes will be destroyed after transcription and the recordings will not be used for any other purposes.

B. Provide a **sample size and a justification** as to how you arrived at that number. If you use screening procedures to arrive at a final sample a table may be helpful.

The third study objective deals with clinical actions for complications and requires the largest sample size due to the rarity of complications. We describe inputs to sample size as shown in Table 1.

Inputs to the sample size calculation are as follows:

- *Number of sites*: The available 12 sites (6 in each study arm) have 1342 births per month, , on average. So 6 facilities have 671 births per month. We believe 80% of these will have a partograph completed during the study.
- *Prevalence*: Kenya QoC report⁹ stated that “19% of labors crossed the partograph ‘action line’”. While this appears high, we also will look for labors with more than one abnormal measurement signaling an early complication. (A study by Orji et al in Nigeria in 2008 also found 18.5% of labors crossed the action line.) For our study, we use the 19% to indicate that up to 19% of labor may cross the action line OR may have 1+ abnormal measurement that signal need for provider action.
- *Average cluster size*: is calculated to be 17.6
- *Intraclass correlation*: ICC is expected to be high as the facilities are a heterogeneous mix of district hospitals, health centers and some private facilities, so we assume ICC of 0.15.
- *Coefficient of variation*: COV is assumed to be 90%, after calculating the standard deviation of the average monthly births in these sites. Therefore, the design effect is high at 5.3, calculated as follows: $1 + ((\text{average cluster size } 16.4 - 1) * (1 + (\text{COV } 0.80^2)) * \text{ICC } 0.15)$.

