Intrapartum death (fresh stillbirth rate) (Tool 5)	Number of fresh stillbirths. This is a count variable.	All live births	Same as above.
Adverse perinatal events (Neonatal deaths <24 hours+ intrapartum death (fresh stillbirth rate))	Number of neonatal deaths and fresh stillbirths	All live births	Same as above.

Statistical analysis plan

Outcomes will be dichotomous, yes/no for each measure.

In the main statistical analysis of our primary outcomes, we will focus on program effect (intervention (ePartogram) group of facilities versus comparison (paper program) group of facilities) as the main predictor of interest. The analysis will be performed at the level of the individual case (partogram). In preliminary analyses we will conduct univariable and bivariable analyses to assess the distribution of key variables and joint distributions and unadjusted relationships.

In final analyses addressing study aims, we will fit multi-level, multivariable regressions models for the outcomes with adjustment for possible confounders and account for clustering by provider and/or study clinic by the use of GEE.

While we have selected clinics roughly matched between the intervention and comparison regions, we will still evaluate confounding to attain the least biased estimate of our intervention effect. Facility level possible confounders are: monthly case load of laboring women, number of providers, key equipment availability etc. Provider-level possible confounders that may be adjusted for are years of work experience since graduation and cadre. Woman-level possible confounders are age and parity.

5. Describe whether you are collecting or storing **personal identifiers**, and if yes, why you need them, and when and how you plan to dispose of them. Signatures on consent forms are considered to be identifiers.

Identifiers of Providers

Our study will assign each facility and each provider a study id number of the Health Worker Line Listing form to be updated monthly. This will be kept separately from partograph data.

partograph review analysis: the paper partograph has a place for a provider to sign it. When we scan/photocopy paper partographs, we will obscure the provider name (cover with lose paper) but will we add/write on it the provider study id number.

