The ePartogram has the potential to improve appropriate use of the partograph and ultimately to improve intrapartum maternal and fetal outcomes. If this study demonstrates ePartogram effectiveness in a clinical setting, it could contribute to efforts to make the ePartogram available widely in resource-challenged settings.

IX. Payment:

- A. Describe the form, amount, and schedule of payment to participants. Reimbursement for travel or other expenses is not “payment,” and if the study will reimburse, explain.
- We tell providers in consent script: “As a SBA, you will receive a per diem of 1750 Kenyan Shillings for each day that you take part in the training workshop. You will also receive 2000 Kenyan Shillings transportation allowance for each round trip to the training site.
- Accommodation and lunch will be provided for the duration of the training.
- If you are selected for and complete the interview, you will receive an additional 500 Kenyan Shillings for your time.”

B. Include the possible total remuneration and any consequences for not completing all phases of the research.

SBAs would receive a maximum of 10750 Kenyan Shillings (~ US\$108) remuneration comprised of 1750 Kenyan Shillings per diem for each of five training days and 2000 Kenyan Shillings for roundtrip ground transportation to the training. Accommodation and lunch will be provided during the trainings. An additional 500 Shillings will be offered to participants completing a qualitative interview; providers can participate in a maximum of 2 qualitative interviews. There are no consequences for providers if they choose to withdraw or not participate in the study at any time.

Facility records management staff person or, in the absence of such a person, the nurse in-charge selected to scan partograph data at the control sites and to photograph maternity registers will receive 2000 Kenyan Shillings (~US\$20) per day worked. Nurse in-charges will work at most 2 hours per day for 5 days in a week, equivalent to 1 day worked per week. Study implementation will take up to 3 months (or 12 weeks). The possible total remuneration for a nurse in-charge is 24,000 Kenyan Shillings (~ US\$240).

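### Section X.D states its aggregate death and stillbirth reporting trigger in two ways that disagree: 2-weekly rates against a baseline rate, and an unscaled monthly total

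*Combined protocol and SAP*

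**What the plan says.** Section X.D, under adverse events expected and unexpected, has four linked bullets.

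- Registers for the three months before the study are scanned to set a baseline for maternal deaths, early newborn deaths and fresh stillbirths.
- Every 2 weeks a register scan is obtained from each facility, and "We will determine the appropriate rates and whether any are more than 10% above the expected/normal rate".
- The third bullet sets the period that the record covers: "A summary log will be created for recording the number of deliveries, births, and adverse maternal or newborn outcomes for each 2 week period". If levels are normal, the log goes to the IRB with the progress report.
- The last bullet gives the condition for escalation: "If the normal level is exceeded (>10% higher than the average monthly total from 3 months prior to the intervention"). Crossing it leads to an SAE report and expedited reporting to the IRB.

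The documents give no baseline death or stillbirth rate. The available text does not say whether the comparison is by facility, by arm or overall. Part of Section X is absent from the public document, so the unit may be stated there.

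Two other places bear on the baseline. In Section III.A, item 4b says of the training given in both groups: "This training will cover how to fill out the Ministry of Health register on each woman/newborn". Item 9b adds that at visits "the study coordinator will orient providers on how to record in the MOH register book, if this is not occurring to standard".

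**The concern.** The second bullet compares rates. The fourth compares with a total that has no births denominator and covers a month, while the log it is judged from covers 2 weeks. No sentence converts one to the other. Two people applying the two bullets to the same log line could reach opposite decisions on whether the IRB is told.

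Each reading has its own weakness. With few events per fortnight, a 10% margin on a rate lies inside chance variation, so many crossings would carry no information. A 2-week count set against a monthly total has the reverse problem and would rarely cross at all.

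The baseline registers also predate the register training and the correction at visits. Recorded events could therefore rise without any change in true events.

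**Working it through.** The plan states no false-alarm rate, so there is no figure of its own to reproduce.

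**Inputs from the documents.** For one arm, "So 6 facilities have 671 births per month" (Section III.B). Births per 2 weeks are 671 × 12 × 14/365.25 = 308.6, and births in the 3 baseline months are 3 × 671 = 2,013.

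**Assumed.** The event rate r is 5-50 per 1,000 births, for one outcome or the composite. Counts are Poisson, with X ~ Poisson(308.6 r m) in a fortnight and B ~ Poisson(2,013 r) at baseline; m = 1 means no change and m = 2 a doubling.

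**Where the two limits sit.** As rates, the limit is 1.1 times baseline. As a 2-week count against a monthly total, it is 1.1 × 671/308.6 = 2.39 times baseline.

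**Example.** Take 40 baseline events, about 20 per 1,000. The rate limit is 1.1 × 40 × 308.6/2,013 = 6.7, crossed at 7 events. The monthly-total limit is 1.1 × 40/3 = 14.7, crossed at 15. A fortnight with 7 to 14 events is reportable under the second bullet and not under a literal reading of the fourth.

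**Probability of crossing in a fortnight**, one arm, baseline estimated from 3 months:

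| Assumed events per 1,000 births | 10 | 20 | 40 |
|---|---|---|---|
| Expected events per fortnight | 3.1 | 6.2 | 12.3 |
| Rates, X/308.6 > 1.1 B/2,013, no change | 0.40 | 0.39 | 0.37 |
| 2-week count, X > 1.1 B/3, no change | 0.042 | 0.007 | 0.0003 |
| 2-week count, X > 1.1 B/3, rate doubled | 0.33 | 0.28 | 0.21 |
| Month against month, no change | 0.40 | 0.37 | 0.33 |

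**Sensitivity of the rate reading to what the documents leave open.** No true change, 5-50 events per 1,000:

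| Unit | Baseline estimated from 3 months | Baseline treated as known |
|---|---|---|
| All 12 sites pooled | 30-40% | 26-43% |
| One arm | 35-40% | 29-46% |
| Average facility | 23-40% | 23-54% |

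If each of the three outcomes is checked separately, as the word *any* suggests, at least one crosses in about 58-82% of fortnights (baseline known, outcomes taken as independent).

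**Does the assumed rate drive this?** By normal approximation, holding chance crossings to 20% for one arm needs r = z²(1/308.6 + 1.21/2,013)/0.01 with z = 0.842. That gives r = 0.272, or 84 events per fortnight. No plausible event rate makes a 10% margin distinguishable from chance in a single fortnight.

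**Recording.** Recorded events reach the limit in expectation once register completeness rises by a tenth in relative terms: from 80% to 88%, or from 90% to 99%. The documents give no completeness figure, so this shows only how small a change would suffice.

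**The case against.** Four points can be made for the plan.

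1. *The fourth bullet may only describe how the baseline is averaged.* A user of the log would probably notice that 2 weeks and a month do not match. Compared month with month, chance crossing is 33-40%, close to the rate reading, and the bullets nearly agree. This stands in part. A reader might infer that the plan would let a doubled death rate go unreported. That needs the most literal reading, and the documents do not show it was meant. They do not exclude it either, because the log is fortnightly and no scaling is stated.

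2. *A sensitive trigger is legitimate.* Crossing leads to a report; Section X.D attaches no stopping or other study action to it. Under the rate reading, a 50% rise is flagged at least once in six looks with probability 0.99 or more, and a doubling within 4 weeks with 0.97 or more (one arm, 10-40 per 1,000). This stands. A reader might infer that the 10% margin must give way to a significance rule. Reporting only when the exact one-sided 97.5% lower limit of the cumulative rate ratio exceeds 1 would hold false reports to 4-5% per arm over six looks. It would, however, find a 50% rise by 12 weeks with probability only 0.33, 0.56 or 0.83. That trade belongs to the investigators and the IRB.

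3. *Individual SAEs are still reported* under the reporting part of Section X.D. This stands, and it limits the severity.

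4. *The recording effect is unquantified.* Agreed. It is a reason to show both arms, not evidence of bias.

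**Conclusion.** The two wordings disagree in the current text, and that does not depend on any assumption. Taken literally, they put the limit at 1.1 and at about 2.4 times baseline.

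The sizes are conditional. With one arm and 10-40 events per 1,000 births assumed, the literal monthly-total reading flags a doubling in about 20-35% of fortnights. With 5-50 per 1,000 assumed, the rate reading crosses by chance in roughly 25-50% of fortnights, and in about 35-40% for one arm with a 3-month estimated baseline. A reader might quote a narrow figure such as 37-40%, or say that nine studies in ten would send a false report, as properties of the plan. The documents do not support that: they give no event rate, and the available text gives no unit of comparison. The nine-in-ten figure (0.88-0.90) is for one arm at 10-40 per 1,000 over six looks, from the 12-week length in Section IX.B.

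Minor to moderate: the aggregate signal cannot be applied consistently as written, while individual SAE reporting and the primary analyses are untouched.

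**What to change.** Use one rule in both bullets. For each of early newborn deaths, fresh stillbirths and maternal deaths, take events per birth in the 2-week period (or cumulatively since the start; state which). Compare it with the same unit's events per birth over the 3 baseline months. Name the unit, and delete the monthly-total wording.

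Keep the 10% crossing as the prompt to report. In each report, show the cumulative rate ratio with its exact confidence interval, and the other arm's ratio beside it. The interval shows how far chance could explain the crossing. The other arm helps to separate better recording from a real rise, because register training is given in both groups.

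The cost is two reworded bullets and a little extra calculation at each look; the data, log and schedule stay the same. The drawback is that chance crossings will still generate reports. Replacing the 10% prompt with a confidence-limit rule is optional, for the reason given above.
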